## 2. Methods

### 2.1 Study Design

In this comparative effectiveness trial (11/2016-10/2019), at-risk Latino adult men will be randomized to one of two arms: (1) HOMBRE, a behavioral lifestyle intervention tailored for Latino men, or (2) a minimal intensity intervention. The study utilizes the RE-AIM (Reach,

Effectiveness, Adoption, Implementation, and Maintenance) framework to systematically assess the potential for implementation and dissemination over time. The specific aims are:

**Aim 1:** Compare the effectiveness of HOMBRE with a minimal intensity intervention for sustaining clinically significant weight loss among overweight and obese Latino men at 18 months.

**Hypothesis:** A significantly higher percentage of overweight and obese Latino men randomized to the HOMBRE intervention will maintain clinically significant weight loss ( $\geq 5\%$  of baseline weight) compared with those randomized to the minimal intensity intervention. Research staff will objectively measure participant weights at baseline and 18 months.

**Exploratory Aim 1:** Compare weight trajectories of Latino men randomized to HOMBRE and the minimal intensity intervention over 18 months and 24 months. Although participants will be followed until 18 months in the study, longitudinal weight data from the electronic health record (EHR) will be abstracted through 24 months post randomization.

**Aim 2:** Compare the effectiveness of HOMBRE with a minimal intensity intervention for improving cardiometabolic risk factors, health behaviors, and psychosocial well-being among overweight and obese Latino men at 18 months.

**Hypothesis:** Compared with Latino men randomized to the minimal intensity intervention, HOMBRE participants will demonstrate statistically significant greater improvements in cardiometabolic indicators (blood pressure, waist circumference), health behaviors (diet, physical activity, sedentary behavior), and psychosocial well-being (quality of life and depressive symptoms) at 18 months.

**Exploratory Aim 2:** Examine potential moderators assessed at baseline (e.g., marital status, acculturation, health literacy) and theoretically-based mediators assessed at 6 and 12 months (e.g., self-efficacy, social support) of the effectiveness of HOMBRE compared to the minimal intensity intervention.

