#### 2.2.7.1 Primary and Secondary Outcomes

The primary outcome is proportion of participants who sustain at least 5% of baseline weight loss at 18 months. Research assistants will weigh participants in duplicate using a standard

calibrated scale at baseline and 18 months at local clinic sites as in previous and ongoing trials. The primary outcome was selected based on its clinical relevance for patients, providers, and health care systems, as well as patient and stakeholder input. Weight loss of  $\geq 5\%$  of baseline weight is known to confer a reduction in risk of diabetes and other chronic disease. This outcome emphasizes chronic disease prevention by focusing on clinically relevant weight loss. Our patient advisors advocated for this primary outcome because their primary goal for the intervention is to reduce the risk for chronic disease. We will examine three types of secondary outcomes:

**Health behaviors** (dietary intake, physical activity, and sedentary behavior) and psychosocial well being will be collected via phone or online questionnaire at baseline, 6, 12, and 18 months (Aim 2). Dietary intake will be assessed using the gold-standard approach of multiple pass 24-hour recalls in Spanish or English by highly trained and experienced staff, over the phone, at baseline and 18 months. Physical activity and sedentary behavior will be assessed using the interviewer-administered 7-day Physical Activity Recall and a self-report measure of sedentary behavior over the phone at all time points. Participants will complete online questionnaires that we have successfully used in prior trials to assess psychosocial well-being (e.g., EuroQol EQ-5D, PHQ-9 for depression). If needed, a research assistant can help a participant fill out the online questionnaire at an office visit.

**Cardiometabolic risk factors** (blood pressure and waist circumference) measured at baseline and 18 months (Aim 2). Trained research assistants will conduct blood pressure and waist circumference measurement according to standard protocols. Waist circumference will be measured in duplicate at the right iliac crest, in centimeters as per previously published protocols.

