**Body Weight from the EHR up to 24 months post-randomization.** We will abstract weight measurements from the EHR 3 months prior to randomization and up to 24 months post-randomization to examine trajectories of weight loss over time. We examined the feasibility of this approach by comparing data on researcher-measured weights and EHR-weights in two prior behavioral lifestyle intervention trials. Using data from two prior trials we observed that participants had a sufficient number of weight measurements in the EHR and there was excellent agreement between researcher-measured weights and weight obtained in the EHR.

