### 2.2.9 Statistical Analysis

#### 2.2.9.1 Analytical Plan

Aim 1 and 2: The primary hypothesis that HOMBRE will lead to a greater percentage of Latino men who sustain  $\geq 5\%$  of baseline weight loss through 18 months than the minimal intensity intervention control group will be tested with a generalized linear mixed model.

$$Y = \beta_0 + \beta_1 X + \beta_2 Y_0 + \sum \beta_{4+i} Z_i + \alpha + \gamma + e \quad (1)$$

Let  $Y$  be the outcome of interest for a patient randomized to arm  $X$  (HOMBRE or control). Given the covariate-adaptive randomization, distributions of baseline values on the outcome variable ( $Y_0$ ) and key characteristics ( $Z_i$ ) should be similar between study arms and thus not bias the results. But to the extent they are associated with the outcome, their inclusion in the analysis will account for otherwise unexplained variation and hence increase efficiency.  $\alpha$  and  $\gamma$  are clinic and PCP nested within clinic random effects, and  $e$  is the random error term. Aim 2 examining secondary outcomes at 18 can be evaluated by adapting the same model. The outcome variables in Aim 2 (e.g., cardiometabolic, health behavior, and psychosocial well-being indicators) will be continuous. We will model the change from baseline in each indicator as the outcome  $Y$  and the fixed and random effects will remain the same as described in model (1).

Primary analyses will follow intent to treat principles. We will verify that mixed model-based results are not sensitive to violations of model assumptions with permutation and bootstrap resampling tests. We will document the extent, pattern, and reasons for missing data, and will conduct sensitivity analyses of the impact of missing data on stability of the primary results. For example, we may use weight data up to the point when they are no longer available (e.g., dropouts) or should not be used, and then employ multiple imputation based on a predictive distribution for future weights.

Exploratory Aim 1: Weight loss trajectories using weight data from the EHR will be examined using tests of group-by-time interactions in mixed-effects growth curve model.

$$Y_t = \beta_0 + \beta_1 X + \beta_2 Y_0 + (\beta_3 + \beta_4 X) T + \sum \beta_{4+i} Z_i + \alpha + \gamma + b_0 + b_1 T + \varepsilon \quad (2)$$

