Let  $Y_t$  be the outcome of interest at follow-up time  $T$  on a patient randomized to arm  $X$  (HOMBRE or control). Baseline values on the outcome variable ( $Y_0$ ) and key characteristics ( $Z_i$ ) will be included for efficiency as in model 1.  $\alpha$  and  $\gamma$  are clinic and PCP nested within clinic random effects as in model 1,  $b_0$  and  $b_1$  account for random intercepts and random slopes, and  $\varepsilon$  is the random error term. We will use a goodness-of-fit test to determine whether to include the quadratic or higher order of growth curves.

Exploratory Aim 2: We will also conduct exploratory subgroup analyses to evaluate potential effect modifiers for the primary outcomes by expanding equation 1 to include appropriate modifier-by-group interaction terms. In this context, testing whether the  $\beta$  coefficients of the interaction terms are equal to zero is equivalent to testing the null hypothesis that the variable of interest does not independently modify the intervention effect. Mediation (e.g., change in self-efficacy and its mediating effect on weight loss outcome) will be examined by MacKinnon's product of coefficients test ( $\alpha\beta$ ). Asymmetric confidence limits will be constructed based on the distribution of the product with the PRODCLIN program. Because multicollinearity may be present in multiple mediator models, we first will test each mediator in single-mediator models. Multiple-mediator models including all variables that are at least marginally significant in the single-mediator models will test for independent and suppression effects. To determine the extent of mediated effect, the percentage of total effect mediated will be calculated for each significant mediator as  $\alpha\beta/(\alpha\beta + \gamma)$ , where  $\gamma$  is the direct intervention effect on outcome. The effect modification-mediation analyses are hypothesis-generating, but we pre-specify the variables to ensure a focus.

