#### 2.2.11 Data Management and Quality Control

All study data will be entered into computerized data files utilizing: (1) Microsoft ACCESS for data entry on recruitment, follow-up, and intervention tracking; (2) WorldApp hosted at PAMF for self- and interviewer-administered questionnaire data and physical measurements; (3) the Nutrition Data System for Research (NDS-R) (Minneapolis, MN) licensed for data collection and nutrient analysis based on multiple-pass 24-hour diet recalls; and (4) a custom-designed web application for seven-day physical activity recall. WorldApp provides convenient multi-lingual functionality that allows participants to easily choose their preferred language for data collection. All data entry systems employ automatic, real-time range, logic, and missing value

checks. Also, the outcome assessors are trained on data collection protocols (e.g., multiple-pass 24-hour diet recall using NDS-R and 7-day physical activity recall), and their performance will be continuously monitored. Data sets will be cleaned, verified and archived, and then placed into SAS (version 9.2, SAS Institute, Cary, NC) data sets, which also will be archived. One official copy of all study data and a master data dictionary will be maintained and updated regularly by the study data analyst. All analytic and tracking databases will be stored in a password-protected, encrypted network drive with continuous backups. For the protection of participant confidentiality, unique anonymous study IDs will be used for data storing, tracking and reporting. Protected health information will be stored separately from all other study data, and used and disclosed in accordance with the Health Insurance Portability and Accountability Act regulations. Regular reports will be produced on (1) patient accrual and follow-up completion/retention in relation to goals and timeline; (2) the randomization process and group comparability on the balancing variables; (3) key baseline characteristics of the sample, by (blinded) group, related to the primary and secondary outcome variables and proposed effect modifiers and mediators; (4) intervention exposure and adherence; and (5) protocol violations. Any observed delays in these processes or data irregularities will be resolved in a timely manner.

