The primary care setting is ideal for capitalizing on this primary motivation for weight loss. However, there is limited research to inform primary care-based implementations. The participation of Latino men in behavioral lifestyle intervention trials based in primary care is difficult to quantify because ethnicity is not usually reported by sex. A systematic review documented only 546 Latino men (4%) among 15,356 participants in behavioral lifestyle intervention trials (not limited to primary care) where race/ethnicity was reported by sex. It is possible that men have not been the focus of primary care-based interventions because they utilize healthcare less often than women. While men may not use healthcare frequently, they still report a known usual place for medical care. Studies have shown that 86% of men age 45-64 years and 96% of men ≥65 years report a known usual place for medical care (excludes emergency room). Benefits of the primary care setting include potential for scalability given policy support for lifestyle interventions. The US Preventive Services Task Force recommends

referral to behavioral lifestyle interventions for obese individuals and for overweight individuals with 1 or more risk factors (diabetes, pre-diabetes, hypertension, dyslipidemia, and elevated waist circumference) encountered in primary care. Additionally, the Center for Medicaid Services reimbursement policies support implementation of behavioral lifestyle interventions in the context of primary care. In addition to policy support, implementation in primary care offers the benefit of leveraging PCP support for adoption and maintenance of behavior change.

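### Exploratory Aim 1's trajectory model, as written, takes follow-up weights from the EHR and leaves out the 18-month research weight, so it is less precise than the collected data allow

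*Combined protocol and SAP*

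**What the plan says.** Section 2.1 sets Exploratory Aim 1: "Compare weight trajectories of Latino men randomized to HOMBRE and the minimal intensity intervention over 18 months and 24 months". Section 2.2.7.1 says that EHR weights are abstracted from 3 months before randomization and "up to 24 months post-randomization to examine trajectories of weight loss over time". Section 2.2.9.1 then gives the analysis: "Weight loss trajectories using weight data from the EHR will be examined using tests of group-by-time interactions in mixed-effects growth curve model".

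In model (2) baseline weight is a covariate, and Y_t is defined to "be the outcome of interest at follow-up time" T. Only weights after randomization therefore form outcome rows.

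The research weight is a separate measurement. Men are weighed in duplicate on a "calibrated scale at baseline and 18 months at local clinic sites" (2.2.7.1), and Table 4 assigns that in-person weight to the primary outcome. Section 2.2.11 lists "WorldApp hosted at PAMF for self- and interviewer-administered questionnaire data and physical measurements", so this weight sits in the study database and not in the abstracted EHR file.

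In support of EHR weights, 2.2.7.1 reports that participants in two prior trials had enough of them and that "there was excellent agreement between researcher-measured weights and weight obtained in the EHR". It gives no count per man.

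**The concern.** The aim covers 18 and 24 months, and at month 18 the trial collects a weight at a visit fixed by protocol, taken by blinded assessors on a calibrated scale. An analyst who follows 2.2.9.1 as written would fit the trajectory without it. Two things would be lost: all outcome information from any man who has a research weight but no follow-up EHR weight, and a well-placed late observation for every other retained man. Both the group-by-time test and the arm difference at month 18 would have larger standard errors than the trial's own data support. The plan's reported agreement between the two sources removes the obvious reason for keeping them apart.

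**Working it through.** **The plan's own figure.** The documents give no precision or sample size for model (2). The 80% retention input comes from the primary calculation in 2.2.10, which reproduces. The control rate is given only as slightly below 39%; I take 35% versus 50%. Then n = [1.960·√(2·0.425·0.575) + 0.842·√(0.35·0.65 + 0.50·0.50)]² / 0.15² ≈ 169.3, that is 170 evaluable per arm. 170/0.8 = 212.5, or 213, against the stated 212.

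**Weights left out.** 0.80 × 424 = 339 men are planned to have an 18-month research weight.

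**Assumptions, because the documents give no values.** Random-intercept SD 3 kg, slope SD 3 kg per year, uncorrelated. Residual SD 2 kg for both sources. EHR visit times uniform over 0-24 months. The number of EHR weights per man is Poisson (even use of care) or negative binomial with dispersion 1 (uneven use). 80% of men have the 18-month weight, independently of EHR visits. Covariates and clinic and provider effects are omitted.

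**Formula.** With time in years, man i has design X_i with rows (1, t) and covariance V_i = X_i·diag(9, 9)·X_i' + 4·I. Information per arm is J = Σ X_i' V_i⁻¹ X_i over 212 men. SE of an arm difference = √(2·c'J⁻¹c), with c = (1, 1.5) for month 18 and c = (0, 1) for the slope. A source indicator common to both arms cancels from the arm difference.

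**Why the gain fades with more EHR weights.** If every man's line were known exactly, the month-18 variance per man would be 9 + 1.5²·9 = 29.25, giving a floor of √(2·29.25/212) = 0.525 kg. One research weight alone has variance 29.25 + 4 = 33.25. It therefore recovers most of what a man with no EHR weights could contribute, and adds little for a man with many.

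**Share of men with no EHR weight.** Poisson: e^(−m). Negative binomial: 1/(1 + m). At m = 3 these are 5% and 25%, or about 21 and 106 of 424 men. Under independence, 80% of them (about 17 and 85) would be recovered.

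**SE at month 18 (kg), EHR only → with research weight:**
- Poisson, mean 3: 0.587 → 0.550, a cut of 6%.
- Negative binomial, mean 3: 0.666 → 0.564, a cut of 15%.
- Negative binomial, mean 2: 0.720 → 0.571, a cut of 21%.
- Poisson, mean 6: 0.544 → 0.537, a cut of 1%.

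| Mean EHR weights in 24 months | Men with none | Cut in SE, month 18 | Cut in SE, slope |
|---|---|---|---|
| 2 | 14-33% | 12-21% | 16-18% |
| 3 | 5-25% | 6-15% | 9-14% |
| 4 | 2-20% | 3-12% | 6-11% |
| 6 | 0-14% | 1-8% | 3-8% |
| 8-10 | 0-11% | 0.3-6% | 1-6% |

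The low end of each range is Poisson and the high end negative binomial. Visit patterns are simulated, so the third decimal of an SE moves slightly between runs.

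**Other assumptions.** Still more uneven visits (dispersion 2) give a cut of 21% at mean 3. A second set of variances (intercept SD 2.5 kg, slope SD 5.5 kg per 18 months, EHR residual SD 1.5-2.0 kg, research residual SD 1.0 kg, 0-30% of men without EHR weights) gives cuts from under 1% (about 8 weights per man, none lacking) to about 29% (about 1 per man, 30% lacking).

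**The case against.** **The text excludes nothing.** Section 2.2.9.1 names EHR weights but does not say that research weights are barred, and the Discussion describes EHR data as a supplement to the in-person visits. This stands: a reader might infer a deliberate exclusion, and the documents do not state one. EHR-only remains the natural reading of 2.1, 2.2.7.1 and 2.2.9.1.

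**EHR weights may be plentiful.** Section 2.2.7.1 reports enough of them in two prior trials. If that carries over, the gain is small. This also stands, and it is why the size is given as a range. The Discussion's remark, "While men may not use healthcare frequently, they still report a known usual place for medical care", concerns men in general. It does not show that these participants, who were found through the EHR and approved by a primary care provider, have few weights. The sparse scenarios are assumptions.

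**Independence may flatter the gain.** The 18-month visit is at a clinic, and men who avoid clinics may miss it too. This stands as a limit on the figures.

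**Bias.** A reader might infer that the EHR-only trajectory is biased toward men who seek care, and that the extra weight cures it. The documents quantify no such bias. One added weight leaves every other time point dependent on care-driven visits, and retention at 18 months is itself selective.

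**Conflict with the primary result.** A reader might also treat disagreement between the month-18 trajectory estimate and the primary result as a sign of a flaw. The primary outcome is a binary 5% responder rate and model (2) describes weight over time, so the two can differ even on identical data.

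**Wrong quantity.** The planned test is the group-by-time interaction, not the month-18 difference. The slope column shows that the gain there is similar.

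**Conclusion.** The point holds as one of precision. Followed as written, model (2) leaves about 339 planned research weights unused and drops any man without a follow-up EHR weight. Adding the weight lowered the standard error in every scenario examined. The size cannot be fixed from the documents: it is material at 2-3 EHR weights per man (6-21% at month 18), modest at 6 (1-8%) and small at 8-10 (0.3-6%), all under the assumed variances and independent 18-month attendance.

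Table 4 lists EHR weight among the secondary outcomes, but the only analysis stated for it is this exploratory one. The primary comparison already uses the research weight and does not change. This is a worthwhile, low-cost improvement and not a threat to the trial's main conclusion.

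**What to change.** In 2.2.9.1, with a matching sentence in 2.2.7.1:
- Define Y_t in model (2) as all follow-up EHR weights plus the research-measured 18-month weight, with a fixed indicator for source (research or EHR).
- Keep the EHR-only fit as a sensitivity analysis.
- Report by arm the number of men with no follow-up EHR weight, so that a reader can place the trial within the range above.

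The cost is SAP wording and at most one extra record per man; no new data are needed. If EHR weights prove plentiful, the two fits should differ little in precision and nothing is lost.

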#### 2.2.7.2 Potential effect modifiers and mediators

We will collect information on potential effect modifiers at baseline including demographic characteristics (e.g., race/ethnicity, marital status, education), technology utilization, and health literacy. For technology utilization, we adapted a survey from the Pew Hispanic Trust on technology access and usage. For health literacy, we will use the newest vital sign, which uses a food nutrition label. Additionally, at each time period, we will collect information on theoretically-based core constructs shown to predict weight loss and behavior change in diverse populations including outcome expectancy, self-efficacy, and social support. These putative mediators are directly informed by Social Cognitive Theory, the theoretical base of HOMBRE and the GLB.

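### The percentage-mediated formula does not say which model supplies its terms, and in the planned multiple-mediator model its denominator is not the total effect

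*Combined protocol and SAP*

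**What the plan says.** All of this is in the combined protocol and SAP, section 2.2.9.1, Exploratory Aim 2, unless stated otherwise.

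- Mediation "will be examined by MacKinnon's product of coefficients test", with asymmetric confidence limits from PRODCLIN.
- Because the mediators may be collinear, "we first will test each mediator in single-mediator models".
- Next: "Multiple-mediator models including all variables that are at least marginally significant in the single-mediator models will test for independent and suppression effects".
- The sentence after that gives the measure of extent: "the percentage of total effect mediated will be calculated for each significant mediator as" αβ/(αβ + γ), where γ "is the direct intervention effect on outcome". No other formula is given. The text does not say whether α, β and γ come from the single-mediator or the multiple-mediator fit.
- Section 2.2.7.2 names the constructs, "including outcome expectancy, self-efficacy, and social support", so up to three or more mediators could enter one model. Table 4 lists more than one scale for some of them.
- The mediation outcome is described only in general terms as weight loss. The primary outcome in section 2.2.7.1 is binary: "The primary outcome is proportion of participants who sustain at least 5% of baseline weight loss at 18 months".
- On status: "The effect modification-mediation analyses are hypothesis-generating, but we pre-specify the variables to ensure a focus".

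**The concern.** The ratio is labelled as a share of the total effect, so its denominator has to be the total effect. Whether it is depends on the model. With one mediator, the effect of arm splits into αβ and γ, and the denominator is complete. With several mediators in one model, γ is what remains after all of them are taken out, so αβ + γ for one mediator leaves out the part carried by the others. The formula's position, right after the multiple-mediator sentence, makes that second use the natural one.

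The percentages are the plan's only stated measure of how much of the HOMBRE effect runs through each mechanism. If their denominators differ from one mediator to the next, they are not shares of a common total, and mechanisms cannot be compared on them. Two analysts could also follow the plan and report different figures for the same mediator.

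**Working it through.** **Inputs.** The formula and the order of modelling come from section 2.2.9.1. The documents state no mediation result and no indirect or direct effect sizes, so there is no figure to reproduce. All effect sizes below are assumptions chosen to show a range.

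**Step 1: algebra (linear models, same participants and covariates throughout).** Write I_k = α_kβ_k.

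- Single-mediator model: total = I + γ. The plan's ratio I/(I + γ) is the share of the total. In a simulated data set of 400,000 with three mediators, I + γ was 0.997 for each mediator, and the separately fitted total effect was also 0.997.
- Multiple-mediator model: total = γ + ΣI_j. The plan's ratio is I_k/(I_k + γ); the share of the total is I_k/(γ + ΣI_j).
- The plan's ratio divided by the correct share is (γ + ΣI_j)/(I_k + γ) = 1 + (sum of the other indirect effects)/(I_k + γ). This exceeds 1 whenever all effects have one sign. If the other indirect effects sum to the opposite sign from I_k + γ, it falls below 1. If I_k and γ nearly cancel, it becomes extreme.

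**Step 2: assumed effects in the multiple-mediator model.**

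| Indirect effects | Direct | Total | Plan's formula | Share of total |
|---|---|---|---|---|
| 0.1, 0.1, 0.1 | 0.7 | 1.0 | 0.1/0.8 = 12.5% each, sum 37.5% | 0.1/1.0 = 10% each, sum 30% |
| 0.7, 0.7, 0.7 | 0.9 | 3.0 | 0.7/1.6 = 44% each, sum 131% | 0.7/3.0 = 23% each, sum 70% |
| 0.9, -0.5 | 0.6 | 1.0 | 0.9/1.5 = 60%; -0.5/0.1 = -500% | 0.9/1.0 = 90%; -0.5/1.0 = -50% |

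In the third row the first mediator's share is understated and the second's is ten times too large in absolute size. A simulation with one opposing mediator (assumed indirect effects 0.4 and -0.2, direct 0.8) showed the same pattern: 33.5% and -33.4% by the plan's formula against 40.2% and -20.0%.

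**Step 3: the single-mediator reading with correlated mediators.** Take three mediators with unit residual variance, residual correlation 0.5, α = 0.5 and β = 0.4 each, and direct effect 0.4. The total is 3 × 0.5 × 0.4 + 0.4 = 1.0. With only one mediator in the model, its coefficient becomes 0.4 + 0.5 × (0.4 + 0.4) = 0.8. The ratio is then 0.5 × 0.8/1.0 = 40%, and the three sum to 120%. The denominator is right here; the shares overlap because each mediator picks up part of what the others carry. In the multiple-mediator model the share of the total is 0.5 × 0.4/1.0 = 20% each, sum 60%, and the plan's formula gives 0.2/0.6 = 33% each.

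**Step 4: a binary outcome.** With a logistic model for a binary outcome and uncorrelated mediators (same α, β and direct effect, now on the logit scale), the simulated αβ + γ in each single-mediator model was about 0.934, against a fitted total effect of 0.905. In the multiple-mediator model the sum of all terms was 1.0. On the logit scale the decomposition is therefore only approximate, even with one mediator.

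**The case against.** The strongest reply is that the plan never ties the formula to the multiple-mediator model. Single-mediator models are also planned, the formula is exact there for a linear outcome, and γ in such a model is properly that model's direct effect. This stands: what the documents support is an unspecified source model, with a wrong denominator under one of the two readings. It does not remove the point, because the sentence follows directly on the multiple-mediator step and no separate formula is given for it.

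Three stronger readings are tempting and are not supported.

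- *Every percentage is overstated.* This holds in the multiple-mediator model when all effects share a sign. It fails under suppression, as 60% against 90% shows, and the plan says that it will test for suppression.
- *A sum above 100% shows that the denominator is wrong.* Step 3 reaches 120% with the right denominator, and the first row of step 2 has the wrong denominator with a sum of only 37.5%.
- *The percentages will decide what later programs contain.* The plan says nothing of the kind. It calls the analyses hypothesis-generating, and the test itself rests on the product of coefficients and its confidence limits. The percentage is a descriptive addition.

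The size of the error also depends on assumed effects. With weak mediation it is a matter of 2.5 percentage points.

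**Conclusion.** The point holds in a limited form. The plan gives one formula, does not name the model that supplies its terms, and places it where the natural reading makes the denominator incomplete. Under that reading the result is not a percentage of the total effect. With the assumed values, the error ranges from 12.5% against 10%, through 44% against 23%, to -500% against -50%; its direction depends on the signs of the effects. These figures assume a linear outcome model and are illustrations, not forecasts for this trial. Under the single-mediator reading the formula is correct, but percentages for correlated mediators overlap. Correlation is likely here: the plan itself anticipates collinearity, and section 2.2.5.1 describes self-efficacy as strengthened by social support.

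The consequence is confined to a descriptive measure in an exploratory analysis. The primary comparison, the sample size and the mediation test are unaffected.

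**What to change.** Amend Exploratory Aim 2 in section 2.2.9.1 as follows.

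1. State which model supplies α, β and γ for the percentage, and in which model a mediator must be significant to receive one.
2. For the multiple-mediator model, use α_kβ_k/(γ + Σ_j α_jβ_j), and add one combined percentage, Σ_j α_jβ_j/(γ + Σ_j α_jβ_j).
3. Where a mediator's sign opposes the others or the direct effect, report α_kβ_k with the PRODCLIN limits that are already planned, instead of a percentage.
4. If single-mediator percentages are reported, say that they overlap and do not add up.
5. Name the mediation outcome. The decomposition is exact for a linear model, so either use continuous weight change or state that, on the logit scale for the binary 5% endpoint, the percentages are approximate.

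It would help to use separate symbols as well, since α and γ already denote the clinic and PCP random effects in model (1).

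The cost is a few lines of SAP text and a small change in code. No new data are needed. The limit is that, if the binary endpoint is kept, the new denominator is itself only approximate.
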